## Analysis of deaths

In addition to the analyses of deaths included in [Table 9](#) the number (%) of participants in the following categories will be provided:

- Deaths during the treatment-emergent and post-treatment periods by study period and main reason for death.
- Summary of fatal AEs, by primary SOC and PT
  - In context of disease progression (death within 30 days from last study intervention administration and the cause of death is disease progression),
  - In context other than disease progression (death within 30 days from last study intervention administration and for whom cause of death is not disease progression or the death occurred more than 30 days from last study intervention administration and the cause of death is AE).
- An overview of Grade 5 AEs will be provided with the following categories:
  - Grade 5 AE (TEAE and post-treatment),
  - Fatal TEAE (regardless of date of death/period),
    - Grade 5 TEAE with a fatal outcome during the treatment-emergent period,
    - Any Grade TEAE with a fatal outcome during the post-treatment period,
  - Post-treatment Grade 5 AE (excluding a TEAE that worsened to Grade 5 during the posttreatment period).
- Deaths in nonenrolled participants or enrolled but not treated participants.

## Analysis of adverse events of special interest (AESIs) and other AEs of interest

Adverse events of special interest (AESIs) will be defined using eCRF and other AEs of interest will be selected for analyses as indicated in [Table 10](#). Number (%) of participants experiencing at least 1 TEAE will be provided overall for AESI, and for each other event of interest, by SOC and PT (if applicable). The DLTs observed during the DLT-observation period will be listed in the DLT-evaluable population. Tables will be sorted as indicated in [Table 8](#).

**Table 10 - Selections for AESIs and other AEs of interest**

AESIs and other AEs of interest	Selection
AESIs	eCRF AESI specific tick box on the AE page
DLT during DLT observation period	eCRF specific DLT page
Other AEs of interest	
Any AE meeting DLT criteria beyond the DLT observation period	AEs reported on the eCRF DLT page outside the DLT observation period
Corneal events	CMQ "Corneal events compound level" containing the PTs included in both SOC "Eye disorders" and SMQ "Corneal disorders" (Narrow)

AESIs and other AEs of interest	Selection
Ocular/visual symptoms (excluding corneal disorders)	CMQ "Eye disorders exclude corneal disorders" containing PTs included in SOC "Eyes disorders" and excluding PTs in SMQ "Corneal disorders" (Narrow)
Cardiac conduction defects	SMQ "Conduction defects" (Narrow)
Peripheral neuropathy events	SMQ "Peripheral neuropathy" (Narrow and Broad)
Colitis events (excluding infective)	CMQ "Colitis (excluding infective)" containing PTs included in HLT "Colitis (excl infective)"
Hypersensitivity events	SMQ "Hypersensitivity" (Narrow) and adverse event occurring on the day or the day after the infusion
Hepatic disorders adverse events	SMQ "Hepatic Disorders" (Narrow and Broad)
Hematological adverse events	SMQ "Haematopoietic cytopenias" (Narrow and Broad)
AE related to COVID-19 illness	SMQ "COVID-19" (Narrow)

An overview of corneal TEAE will be provided with the following AE categories: any corneal TEAE, Grade  $\geq 3$  corneal TEAE, treatment-emergent corneal SAE, corneal TEAE leading to permanent full study intervention discontinuation, corneal TEAE leading to permanent partial discontinuation of tusamitamab ravtansine, corneal TEAE related to IMP, Grade  $\geq 3$  corneal TEAE related to IMP, and corneal TEAE leading to dose modification of tusamitamab ravtansine (cycle delay, dose omission, or dose reduction).

In addition, a summary table of corneal events will be displayed by grade.

A summary of treatment-emergent corneal events will be provided.

- Number (%) of participants by worst grade.
- Cycle of first onset of corneal event regardless of the grade.
- Cycle of first onset of corneal event with the worst grade.
- Relationship to the study intervention: in case of multiple events with different relationships, if any event is related, then the relationship will be considered as related.
- Action taken with the study intervention: in case of multiple events with different actions, the most severe action taken will be tabulated and selected according to the following order of severity: drug withdrawn, dose reduced, drug interrupted, dose not changed.
- Outcome: in case of multiple events with different outcomes, the most severe outcome will be tabulated and selected according to the following order of severity: fatal, not recovered or resolved, recovering or resolving, recovered or resolved with sequelae, recovered or resolved, unknown.

In addition, analyses on occurrence and recurrence of corneal events will be provided. An occurrence of corneal event is defined as one or a group of concomitant corneal events. A recurrence is defined as any new occurrence of corneal event starting after a previous resolved occurrence.

- The number of occurrences by participant.

- The time to first onset of corneal event will be described using Kaplan-Meier curves. Time to first onset is defined as the time from the date of first IMP administration to the date of the first occurrence of the event. In the absence of an event before the analysis cut-off date, it will be censored at the end date of the treatment-emergent period, analysis cut-off date or date of death, whichever occurs first.
- The time to recovery will be summarized using descriptive statistics in participants who have had at least 1 recovered or resolved occurrence of a corneal event (with or without sequelae), considering the longest duration, and the longest duration of the worst grade among all occurrences by participant.
- The time to recurrence will be summarized using descriptive statistics in participants who have had at least 1 recurrence, considering the shortest time among all recurrences by participant.

Beside the AE categorized as ocular/visual AEs, all ocular symptoms (coded term) recoded in the eCRF will be reported as a descriptive analysis. The same analysis will be done separately on ocular symptoms associated with treatment-emergent corneal events (CMQ).

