2.3 BENEFIT/RISK ASSESSMENT

To date, efficacy and safety data from ongoing studies of tusamitamab ravtansine (TED13751, TCD15054, ACT16146, ACT16444, ACT16525, ACT16432 and EFC15858) support continued clinical development of tusamitamab ravtansine. Information about the known and expected benefits, risks, and reasonably anticipated AEs with tusamitamab ravtansine may be found in the Investigator's Brochure (IB). Based on available safety data, the main anticipated risk to patients is corneal toxicity presenting as microcystic keratopathy/keratitis, which is reversible and manageable with dose delay and dose reduction in some patients. Peripheral neuropathy is an identified risk.

Other potential risks include colitis (including hemorrhagic), cardiotoxicity (myocardial or conduction abnormalities), hematologic cytopenia, and hepatotoxicity, as well as systemic acute hypersensitivity (including anaphylaxis) and, in patients who received tusamitamab ravidansine in peripheral veins, local infusion site reactions to tusamitamab ravidansine (6).

Ramucirumab, a human IgG1 monoclonal antibody that inhibits VEGFR-2, is approved in combination with docetaxel for the treatment of patients with metastatic NSCLC. Given the considerable risks of adverse effects including neutropenia, anemia, and infection associated with docetaxel, the combination of tusamitamab ravidansine with ramucirumab may represent a treatment regimen with an improved safety profile as compared to the approved combination of docetaxel and ramucirumab. More detailed information about the known and expected benefits and risks and reasonably expected adverse effects of ramucirumab may be found in the US Package Insert or Summary of Product Characteristics for Cyramza®.

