After the EOT visit, the **Follow-up (FU) visit** will be performed at 90 (± 7) days after the last infusion. During the FU visit, the participants will be monitored for all ongoing related AEs and all SAEs and AESIs, regardless of relationship until resolution or stabilization (ie, an event ongoing without any change for at least 3 months). All new related AEs, SAEs, or AESIs will be followed until resolution or stabilization. If ongoing IMP-related AEs and all SAEs/AESIs are resolved or stabilized, no further safety follow-up visit will be needed; if not resolved or stabilized, an on-site follow-up visit will be performed every 12 weeks (± 7 days) until resolution or stabilization.

For the doublet cohort, a participant who stopped treatment for a reason other than PD, follow-up visits will be performed every 12 weeks (± 7 days) after the last tumor assessment until documented radiological disease progression, start of a new anticancer therapy, death, study cut-off date of the secondary ORR endpoint of the triplet cohort, or withdrawal of participant's consent (whichever comes first).

The study cut-off for the primary ORR endpoint analysis corresponds to the date on which all evaluable treated patients have had at least 2 postbaseline tumor assessments, experienced confirmed objective response, or have discontinued the study for any reason; the study cut-off can be up to approximately 6 months (4 months for 2 assessments, with an additional 2 months if confirmation of a response is needed) from the date the last participant's first administration.

After the study cut-off date for the primary ORR analysis, if clinical benefit is observed, a patient still receiving study treatment can continue study treatment until PD, unacceptable toxicity, or withdrawal of participant's consent, and will continue to undergo all assessments as per the study flow chart.

Triplet cohort:

Participants will be treated with tusamitamab ravidansine and ramucirumab and pembrolizumab to assess the tolerability of the combination to be used in the subsequent studies. The first 3 participants will receive ramucirumab at 10 mg/kg followed by tusamitamab ravidansine at 150 mg/m² and pembrolizumab at 200 mg every 3 weeks (Q3W). Administration of tusamitamab ravidansine will begin at least 1 hour after completion of ramucirumab infusion.

DLT definition is reported in [Table 5](#).

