#### **4.7.2 Adverse events**

##### **General common rules for adverse events**

All AEs will be graded according to National Cancer Institute Common Terminology for Adverse Events (NCI-CTCAE version 5.0) and coded to a lower-level term (LLT), preferred term (PT), high-level term (HLT), high-level group term (HLGT), and associated primary system organ class (SOC) using the Medical Dictionary for Regulatory Activities (MedDRA) version currently in effect at Sanofi at the time of database lock.

The AEs will be analyzed in the following 3 categories:

- Pre-treatment AEs: AEs that developed, worsened or became serious during the pre-treatment period.
- Treatment-emergent adverse events (TEAEs): AEs that developed, worsened or became serious during the treatment-emergent period.
- Post-treatment AEs: AEs that developed, worsened or became serious during the post-treatment period.

Similarly, the deaths will be analyzed in the pre-treatment, treatment-emergent, and post-treatment periods.

The primary AE analyses will be on TEAEs. Pre-treatment AEs and post-treatment AEs will be described separately.

An AE with incomplete or missing date/time of onset (occurrence, worsening, or becoming serious) will be classified as a TEAE unless there is definitive information to determine it is a pre-treatment or a post-treatment AE.

If the assessment of the relationship to IMP is missing for an AE, this AE will be assumed as related to IMP. Missing grade will be left as missing.

Multiple occurrences of the same event in the same participant will be counted only once in the tables within a treatment phase, using the maximum (worst) grade by treatment phase. Summaries will be provided for all grades combined and for Grade  $\geq 3$  (including Grade 5). Missing grades, if any, will be included in the “all grades” category.

The AE tables will be sorted as indicated in [Table 8](#).

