##### ***Visual acuity test***

Analyses are done on the best corrected visual acuity assessed using Snellen Chart method.

Frequency tables on best corrected visual acuity (BCVA) measured during on-treatment period will be performed separately on all participants and on participants who experienced at least one treatment-emergent corneal event:

- On the worst change from baseline: No worsening versus baseline (no line decrease), Worsening versus baseline 1 to 3 lines decrease versus baseline, or  $> 3$  lines decrease versus baseline).
- On the worst absolute value: No change versus baseline, Worsening versus baseline (BCVA equals to 20/40 or better, BCVA worse than 20/40 up to 20/200, BCVA 20/200 or worse).
- On the CTCAE worst vision decrease: BCVA equals to 20/40 or better or 1 to 3 lines decrease versus baseline, BCVA worse than 20/40 up to 20/200 or  $> 3$  lines decrease versus baseline, BCVA 20/200 or worse.
- For participants who had worsening versus baseline on BCVA (at least one line decrease), the worst outcome on the last BCVA value will be displayed: Recovered to baseline, Not recovered to baseline, Lost to follow-up or dead with ongoing corneal events.

Of note, a participant will be considered as lost to follow-up, if the participant discontinued the study and did not perform any follow-up visit.

A shift table of the category of the last BCVA value (Normal (20/20 or better), worse than 20/20 up to 20/40, worse than 20/40 up to 20/200 or 20/200 or worse) versus the category of the worst BCVA value (20/40 or better, worse than 20/40 up to 20/200, 20/200 or worse) will be performed for participants who experienced at least one treatment-emergent corneal event.

For the summary table on participants who experienced at least one treatment-emergent corneal event, the worst value and the worst change from baseline are measured during any of the treatment-emergent corneal events experienced by the participant (between start date and end date of the corneal events). For the summary table on all participants, all on-treatment BCVA values are considered.

The worst classification between the laterality is considered for the worst value, the worst change from baseline and the last separately even if not measured on the same eye. If the worst absolute value is the same for both eyes, then the eye with the worst change from baseline is considered, and if identical, then the eye with the worst last value is considered.

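### In the corneal-event summary the SAP ranks 'unknown' as the mildest outcome, so a participant with one recovered and one unknown-outcome event is shown as recovered, which can overstate documented recovery

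*SAP*

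**What the plan says.** SAP 4.7.2, in the summary of treatment-emergent corneal events that follows Table 10, gives one outcome per participant: "in case of multiple events with different outcomes, the most severe outcome will be tabulated". The ranking, from most to least severe, is "order of severity: fatal, not recovered or resolved, recovering or resolving, recovered or resolved with sequelae, recovered or resolved, unknown". Nothing else in the SAP or protocol changes this order or asks for a count of participants with any corneal event of unknown outcome.

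The same subsection summarises time to recovery only "in participants who have had at least 1 recovered or resolved occurrence of a corneal event".

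Protocol 2.3 states that "the main anticipated risk to patients is corneal toxicity presenting as microcystic keratopathy/keratitis, which is reversible and manageable". For follow-up, Protocol 4.1 says: "All new related AEs, SAEs, or AESIs will be followed until resolution or stabilization".

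**The concern.** A worst-outcome rule is meant to be conservative: when a participant has several events, the least favourable one is shown. Putting 'unknown' below 'recovered or resolved' makes missing information the most favourable value. An event whose resolution was never documented then disappears behind any event that did resolve.

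Participants with recurrences are one clear case. SAP 4.7.2 defines a recurrence as a new occurrence after an earlier one has resolved, so these participants always have a resolved occurrence on record. If the outcome of the recurrence is unknown, the table cannot show it.

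The SAP is more cautious about missing information elsewhere:

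- **Causality (4.7.2):** "If the assessment of the relationship to IMP is missing for an AE, this AE will be assumed as related to IMP".
- **Response (4.3.2.2):** a participant whose best response cannot be evaluated counts as a non-responder.
- **Immunogenicity (4.8.2):** a participant with any inconclusive sample after first dosing cannot be classed as free of treatment-emergent antibodies.

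At stake is how a reader sees reversibility of the main anticipated toxicity. A table showing nearly everyone as recovered would support the protocol's description, although some of those participants would have an event with no documented resolution.

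**Working it through.** The plan states no figure here, so there is nothing to reproduce. The check applies the stated order literally and then compares two alternatives.

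**Inputs.** The six outcome categories and their order come from SAP 4.7.2. The number treated, about 30 to 36, comes from SAP 1.1. M (participants with at least one corneal event) and k (participants whose events include an unknown outcome and a recovered one, with or without sequelae, and nothing worse) are not in the documents and are assumed below.

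**Step 1: the order as written.** 'Unknown' can be combined with any non-empty subset of the five known outcomes, which gives 2^5 − 1 = 31 mixes. 'Unknown' is selected in 0 of the 31. It appears only when every corneal event of the participant is unknown. The mixes with a single known outcome resolve as follows:

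| Outcomes on record | Tabulated as |
|---|---|
| fatal, unknown | fatal |
| not recovered, unknown | not recovered |
| recovering, unknown | recovering |
| recovered with sequelae, unknown | recovered with sequelae |
| recovered, unknown | recovered |

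The first three still show an unfavourable or unresolved outcome. Only the last two give an impression of recovery.

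**Step 2: 'unknown' placed just above both recovered categories.** The mixes that change are those whose known outcomes are all recovered categories: 2^2 − 1 = 3 of 31. They are recovered + unknown, with sequelae + unknown, and both recovered categories + unknown.

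**Step 3: 'unknown' placed directly after 'not recovered or resolved'.** Now 2^3 − 1 = 7 of 31 change. The additional 7 − 3 = 4 all contain 'recovering', so this order would replace a documented unresolved event with 'unknown'.

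**Step 4: size.** Against the order in step 2, the combined recovered percentage under the SAP is higher by 100 × k/M points. For assumed counts:

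| k | M = 5 | M = 10 | M = 15 |
|---|---|---|---|
| 0 | 0 | 0 | 0 |
| 1 | 20 | 10 | 6.7 |
| 2 | 40 | 20 | 13.3 |
| 3 | 60 | 30 | 20 |

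The difference is never negative, so the rule acts in one direction only.

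**The case against.** The strongest defence is that 'unknown' does not mean unresolved. On that view the rule tabulates the worst documented outcome and falls back on 'unknown' only when nothing is documented. If the unknown event did resolve, nothing is misreported. This stands, and it limits the point to documented recovery.

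Follow-up should also keep unknown outcomes few. Protocol 4.1 follows related events and AESIs to resolution or stabilisation, Protocol 8.3.1 makes Grade ≥3 keratopathy an AESI, and Protocol 8.2.2 and 8.2.6.2 require repeated eye examinations after ocular toxicity. This lowers k but does not make it zero: stabilisation is not resolution, withdrawal and loss to follow-up are foreseen (Protocol 7.2 and 7.3), and the SAP itself lists 'unknown' as a possible outcome.

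Reversibility is also assessed from measured acuity. SAP 4.7.3.2 uses the categories "Recovered to baseline, Not recovered to baseline, Lost to follow-up or dead with ongoing corneal events" and adds a table of last against worst acuity. A reader might infer that the SAP does the opposite there and so contradicts itself. It does not: that row classifies measured acuity in participants who lost at least one line, and it does not rank investigator-coded event outcomes. It is a partial safeguard, because corneal events without acuity loss, and participants excluded for a naked-eye baseline, fall outside it.

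A reader might also infer that the effect sits mainly in participants with recurrences who leave the study. The documents do not show this. SAP 4.7.2 allows an occurrence to be a group of concomitant events, so a mixed record needs neither a recurrence nor a later event.

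**Conclusion.** The point holds as a narrow defect in one descriptive row. The ranking is explicit, nothing overrides it, and it can only raise or leave unchanged the share of participants shown as recovered. Its size is 100 × k/M percentage points, with k and M unknown; it is zero if no participant has such a mixed record. Because M cannot exceed the 30 to 36 treated, even one case would be visible in the table.

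A reader might go further and conclude that the trial will overstate reversibility, or that the benefit-risk conclusion depends on this table. The documents do not support that. The unknown events may have resolved, and the reversibility statement in Protocol 2.3 is background from available safety data. Recovery rate is not an endpoint, SAP 4.7 makes the safety analyses descriptive without testing, and no decision rule uses this row. The response-rate analysis and the dose decision are unaffected.

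**What to change.** Preferred: keep the order for known outcomes and add a row to the corneal-event summary for participants with at least one corneal event of unknown outcome. This needs no judgement on how severe 'unknown' is and hides nothing. The tabulated recovered percentage stays as it is, but the reader can see how far it might rest on undocumented events.

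Alternative: rank 'unknown' after 'recovering or resolving' and above both recovered categories. The recovered percentage may then look slightly less favourable, and a documented 'with sequelae' outcome could be displaced by 'unknown'; the extra row avoids this. 'Unknown' should not be ranked above 'recovering or resolving', because that would hide a documented unresolved event.

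Either change is one line in the SAP and a small programming edit. Making it before database lock avoids a choice made after the outcomes are seen.

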The patient should be asked about ocular/visual symptoms at each visit, and ocular evaluation including visual acuity, slit lamp examination under dilatation, and Schirmer's test should be carried on according to Study Procedures ([Section 1.3](#)). Ocular evaluation will be performed at baseline (during the screening period), as required during the treatment (ie, on occurrence of ocular symptoms such as blurred vision, photophobia, pain), at the EOT visit, and when relevant at follow-up visit(s). The outcome of the examination should be available before infusion of the next cycle. If ocular symptoms are present, then a formal ocular examination should be performed. In patients with any ocular/visual symptom(s) (eg, blurred vision, photophobia), the ocular evaluation should be repeated once weekly, unless less frequent assessment is recommended by an ophthalmologist, until resolution to Grade 1. Subsequently, the participant should be followed with ocular exam (slit lamp and visual acuity) at each cycle until total resolution of the event.

Photographs of the cornea are recommended to be taken at the site, if possible, when ocular findings are first documented, and to follow progression when relevant. Tonometry and additional ocular assessment can be performed at discretion of an ophthalmologist when applicable.

8.2.6.2.1 *Keratopathy/keratitis management*

Reversible non-inflammatory, microcystic keratopathy was identified as the DLT during the dose escalation process in TED13751 study with tusamitamab ravidansine. At slit-lamp examination, it presents as lesions consisting of 100s to 1000s microcysts and/or deposits that are initially observed at the periphery of the cornea, the limbus being preserved. The lesions have a centripetal distribution and evolve towards the center of the corneal upon resolution, following the natural keratinocyte regeneration process.

For standardization of AE verbatim, keratopathy should be preferred term unless otherwise specified by an ophthalmologist due to inflammatory findings on eye exams leading to diagnosis of keratitis.

The potential ocular/visual toxicity symptoms could include, but are not limited to, blurred vision, dry eye, and photophobia. Curative treatment may be used as recommended by an ophthalmologist.

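### Corneal time to recovery is summarised only in participants who recovered, so unresolved occurrences are dropped rather than censored (minor)

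*SAP*

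**What the plan says.** The relevant text is the list on occurrence and recurrence of corneal events in SAP 4.7.2.

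- **Recovery.** "The time to recovery will be summarized using descriptive statistics in participants who have had at least 1 recovered or resolved occurrence". Recovery counts whether or not sequelae remain. The value taken for each participant is defined by "considering the longest duration, and the longest duration of the worst grade among all occurrences by participant".
- **Recurrence.** "A recurrence is defined as any new occurrence of corneal event starting after a previous resolved occurrence".
- **First onset, in the same list.** "The time to first onset of corneal event will be described using Kaplan-Meier curves". Participants without an event are censored at the end of the treatment-emergent period, the analysis cut-off or death, whichever is first.
- **Outcome.** The same section tabulates the most severe outcome per participant, ranked as "fatal, not recovered or resolved, recovering or resolving, recovered or resolved with sequelae, recovered or resolved, unknown".

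SAP 4.7.3.2 adds outcome categories for participants whose visual acuity worsened, including "Not recovered to baseline, Lost to follow-up or dead with ongoing corneal events".

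On follow-up, Protocol 8.2.6.2 asks that participants with ocular symptoms have eye examinations "at each cycle until total resolution of the event". Protocol 4.1 lets safety follow-up end earlier: "If ongoing IMP-related AEs and all SAEs/AESIs are resolved or stabilized, no further safety follow-up visit will be needed". Stabilised there means ongoing without change for at least 3 months.

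**The concern.** How long an event takes to resolve is a time-to-event quantity, and some occurrences will not have ended when observation stops. The SAP handles incomplete observation for onset but not for recovery. For recovery it keeps only participants who reached the event and takes plain descriptive statistics.

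Long-lasting occurrences are the ones most likely to be unresolved when observation stops. Leaving them out therefore tends to pull the reported recovery time down.

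The figure will be read. Protocol 2.3 names corneal toxicity as the main anticipated risk and describes it as reversible, and time to recovery is what a reader would use to judge that description.

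**Working it through.** **1. Is there a rule elsewhere?** Three places in the SAP could supply one, and none does. The general adverse-event rules in 4.7.2 deal with missing onset dates. Section 4.9 ends the treatment-emergent period at the cut-off for participants still on treatment, but gives no end date or censoring for an ongoing event. Appendix 3 (5.3) covers unscheduled visits only.

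**2. Can unresolved occurrences remain?** Yes. The outcome list and the visual acuity categories both provide for them, and follow-up may stop at stabilisation. Death and loss to follow-up also end observation.

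**3. How large is the effect?** The plan has no figure to reproduce: neither document gives a recovery time, a recurrence rate or an unresolved share. Every input below is an assumption.

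Take one occurrence per participant. Let *T* be the time to recovery, with density *f* and a true median of 4 weeks. Let *C* be the observed time after onset, independent of *T* and uniform on (*a*, *b*) weeks. Let *G*(*t*) = P(*C* ≥ *t*), which is 1 up to *a*, then (*b* − *t*)/(*b* − *a*) up to *b*.

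- Unresolved share = 1 − ∫ *f*(*t*) *G*(*t*) d*t* over all *t*.
- The recovered-only median *m* solves ∫ *f*(*t*) *G*(*t*) d*t* from 0 to *m* = half of the same integral over all *t*.
- Shortfall = (4 − *m*)/4.

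By numerical integration:

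| *C* uniform on | Exponential: unresolved, *m*, shortfall | Gamma, shape 4: unresolved, *m*, shortfall |
|---|---|---|
| 12 to 52 weeks | 1.8%, 3.90, 2.6% | 0.0%, 4.00, 0.0% |
| 12 to 24 weeks | 5.3%, 3.70, 7.4% | 0.1%, 4.00, 0.0% |
| 0 to 52 weeks | 11.1%, 3.54, 11.5% | 8.4%, 3.91, 2.3% |
| 0 to 24 weeks | 23.7%, 2.99, 25.2% | 18.2%, 3.79, 5.3% |

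The assumed median matters too. With exponential recovery and at least 12 weeks observed (the first two rows), a 2-week median gives shortfalls of 0.2% and 0.5%, and an 8-week median gives 13.6% and 28.7%.

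**4. What does taking the longest duration do?** It pushes the other way. I simulated up to two exponential occurrences per participant (median 4 weeks each, mean gap 4 weeks, recurrence probability 0.3 or 1, same follow-up patterns, 1,000,000 participants each). The longest-duration median ran from about 3.3 to 6.8 weeks, against 4.0 for a single occurrence. In every one of these exponential scenarios it was below the true median of the participant's longest occurrence.

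**The case against.** The case for leaving the text alone is substantial.

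- **Non-recovery is reported.** The denominator is stated openly, and unresolved outcomes are counted in the outcome table and the visual acuity categories. This stands. A reader might infer that the plan conceals non-recovery; the documents do not support that. The counts carry no durations, however, so they do not repair the recovery-time figure.
- **Follow-up is long.** Eye examinations run until total resolution, related events are followed until resolved or unchanged for at least 3 months, and all analyses are updated at the end of the study. This stands, and it makes the 0-to-24 and 0-to-52-week rows above pessimistic. It does not remove stabilised events, deaths or losses.
- **The direction is not guaranteed.** A reader might infer that the statistic is short whenever any occurrence is unresolved. That does not follow. If an ongoing recurrence would end sooner than the earlier resolved occurrence, that participant's longest duration is unchanged. If durations are nearly constant, selection changes little.
- **Ongoing recurrences.** By the SAP's definition of recurrence, a participant with an ongoing recurrence has an earlier resolved occurrence and so is in the summary, and the wording takes all occurrences. A reader might infer that the derivation is undefined. An event that has not recovered has no time to recovery, so the natural reading is resolved occurrences only. This is a wording clarification and does not carry the point.

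**Conclusion.** The point holds as a minor one. The SAP conditions on recovery when it summarises time to recovery, and it gives no censoring rule. This tends to shorten the figure for the toxicity of most interest.

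The size cannot be found from the documents. For a single occurrence with an assumed 4-week median and independent end of observation, it is about 0% to 5% under gamma shape 4 and about 3% to 25% under exponential recovery. Nothing in the documents favours either shape, so the effect may be negligible. The larger values need observation to stop soon after onset regardless of resolution, which fits the protocol's follow-up rules poorly.

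SAP 4.7 makes the safety analyses descriptive with no testing. No endpoint, test or dose decision uses this statistic.

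**What to change.** Make two changes to SAP 4.7.2.

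1. Add a Kaplan-Meier analysis of time to resolution of the first occurrence in all participants with a treatment-emergent corneal event. The event is recovered or resolved, with or without sequelae. Unresolved occurrences are censored at the last ocular assessment, the analysis cut-off or death, whichever is first. Say in the text that this is a different quantity from the longest duration and does not correct it.
2. Keep the longest-duration summary, state that it uses resolved occurrences only, and show beside it the number of participants with an unresolved occurrence.

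The cost is a few sentences and one extra descriptive table from data already collected. With few corneal events likely among the 30 to 36 treated participants, the confidence interval will be wide. Censoring at death, or at the last assessment of a stabilised event, may be informative, and the table should say so.
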